#### **4.4 End of study definition**

A participant is considered to have completed the study if he/she has completed all periods of the study including the SFU Visit (within 10 days after the last dose for Part A or 7 days after the last dose for Part B).

The end of the study is defined as the date of the last scheduled procedure for the last study participant in the study (see Section 1.3 for details on Schedule of Activities).

### **5 STUDY POPULATION**

Prospective approval of protocol deviations to recruitment and enrollment criteria, also known as protocol waivers or exemptions, is not permitted.

#### **5.1 Inclusion criteria**

Participants are eligible to be included in the study only if all of the following criteria apply:

##### **Age**

1. Participant must be 18 to 55 years of age inclusive at the time of signing the ICF.

##### **Type of participant and disease characteristics**

2. Participants who are overtly healthy as determined by medical evaluation including medical history, physical examination, laboratory tests, and cardiac monitoring.

Note: study participants must have clinical laboratory test results within the local reference ranges or values that are considered as not clinically relevant by the Investigator and approved by the Medical Monitor. Laboratory parameters outside the reference ranges may be retested once and if the retest is within the reference range or considered as clinically not relevant, the study participants will be allowed in the study (Section 5.4).

3. Part A only: all healthy study participants except for those participants who are eligible for Part B of the study.
4. For participants of Japanese origin (Part B): study participant is of Japanese descent as evidenced by appearance and verbal confirmation of familial heritage (a participant has all 4 Japanese grandparents born in Japan).

For participants of Chinese origin (Part B): study participant is of Chinese descent as evidenced by appearance and verbal confirmation of familial heritage (a participant has all 4 Chinese grandparents born in China).

##### **Weight**

5. Body weight within 45 to 100kg (female) and 50 to 100kg (male) and body mass index (BMI) within the range 18 to 30 kg/m^2 (inclusive at screening).

## Sex

6. Healthy male and female study participants
  - A male participant must agree to use contraception as detailed in Appendix 4 of this protocol during the treatment period and for at least 1 week after the last dose of study medication, and refrain from donating sperm during this period (Section 10.4)
  - A female participant is eligible to participate if she is not pregnant (see Appendix 4, Section 10.4), not breastfeeding, and at least one of the following conditions applies:
    - Not a woman of childbearing potential (WOCBP) as defined in Appendix 4
    - OR
    - A WOCBP who agrees to follow the contraceptive guidance in Appendix 4 during the treatment period and for at least 1 week after the last dose of study medication.

## Informed consent

7. Capable of giving signed informed consent as described in Appendix 1 (Section 10.1) which includes compliance with the requirements and restrictions listed in the ICF and in this protocol.

## 5.2 Exclusion criteria

Participants are excluded from the study if any of the following criteria apply:

### Medical conditions

1. Participant has any medical or psychiatric condition that, in the opinion of the Investigator, could jeopardize or would compromise the study participant's ability to participate in this study.
2. Participant has a history or presence of/significant history of cardiovascular, respiratory, hepatic, renal, gastrointestinal, endocrinological, hematological, or neurological disorders capable of significantly altering the absorption, metabolism, or elimination of drugs; constituting a risk when taking the study intervention; or interfering with the interpretation of data.
3. Participant has had lymphoma, leukemia, or any malignancy within the past 5 years, except for basal cell carcinomas that have been resected, squamous epithelial carcinomas of the skin that have been resected with no evidence of metastatic disease for 3 years.
4. Participant has had breast cancer within the past 10 years.
5. Participant has a history of alcohol or drug abuse within the last 1 year from Screening, as defined according to the Diagnostic and Statistical Manual of Mental Disorders.
6. Participant has a known hypersensitivity to any components of the study medication or comparative drugs as stated in this protocol.
7. Participant has a consumption of more than 600mg of caffeine/day at screening and throughout the study (1 cup of coffee contains approximately 100mg of caffeine, 1 cup of tea approximately 30mg, and 1 glass of cola approximately 20mg).

---

8. Participant has consumed any grapefruit, grapefruit juice, grapefruit-containing products, or star fruit within 14 days prior to administration of study medication or is not willing to refrain from consuming these products for the duration of the study.
9. Participant is excluded if any of the following COVID-19 criteria apply:
  - Participant has a positive test result for SARS-CoV-2 using reverse transcription-polymerase chain reaction (RT-PCR) on admission.
  - Participant has clinical signs and symptoms consistent with COVID-19 (eg, fever, dry cough, dyspnea, sore throat, fatigue) or confirmed infection by appropriate laboratory test within the previous 14 days prior to screening or on admission or a history of in-patient hospitalization secondary to COVID-19.
  - Participant is currently in quarantine (has been in contact with a SARS-CoV-2 positive patient in the last 14 days).
  - Participant has had a severe course of COVID-19 (eg, requiring extracorporeal membrane oxygenation, mechanical ventilation or hospitalization).
10. Participant has, in the opinion of the Investigator, a known relevant allergy (not including mild seasonal hay fever and/or conjunctivitis or low-grade food intolerances), a preexisting history of a relevant allergic condition, or a predisposition for an allergic reaction (eg, total immunoglobulin E [IgE] value above normal range at screening).

#### **Prior/concomitant therapy**

11. Participant has received or intends to use any prescription or nonprescription medicines, including enzyme inhibitors or inducers, any gastric pH modifying agents, over the counter remedies, herbal and dietary supplements (including St. John's Wort) up to 2 weeks (4 weeks for enzyme inducers) or 5 half-lives of the respective drug (whichever is longer) before the first administration of study medication and during the clinical part of the study, unless required to treat an AE. Drugs with known CYP3A4 interaction (strong inducers and inhibitors) are prohibited. This does not include oral contraceptives exceeding 30µg ethinyl estradiol or postmenopausal hormone replacement therapy or implants, patches, or intrauterine devices (IUDs)/intrauterine hormone-releasing system (IUSs) delivering progesterone (for female study participants).

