  - Eligible study participants will commence the Treatment Period on Day -1. Each participant enrolled will receive a single oral dose of UCB0599 (formulation selected in Part A) or placebo on Day 1 (90mg or 180mg or 360mg of UCB0599 or matching placebo), in accordance with the randomization schedule (see [Table 1-2](#)). Study participants will be administered the second single oral dose of UCB0599 or placebo on Day 6. In between each Treatment Period, participants will undergo a 4-day Washout Period. During the whole treatment, participants will remain under close medical supervision in the clinic.
- A SFU Period (7 days after the last study medication administration)

In Treatment Period 1 through Period 2 for Part B, study participants will fast overnight for at least 10 hours prior to study medication administration on Day 1 and Day 6, and continue to fast for at least 4 hours post-study medication administration. Thereafter participants will be given a standard breakfast or light snack (see [Table 1-2](#) and [Table 1-4](#)).

On Day 10, after all the scheduled procedures have been performed, the study participant may leave the clinic provided that, in the opinion of the Investigator, there are no safety concerns. Study participants will return to the clinic to complete the SFU assessments. Blood samples for determination of plasma UCB0599 and its [CC1](#) metabolites will be collected over 96 hours postdose (see Schedule of Activities, Section 1.3). Up to a maximum of 6 replacements will be targeted in case participants discontinue Part B (see Section 7).

There is 1 planned interim analysis for Part B in which safety data from Part B will be analyzed (Section 9.8). Throughout the study, data will be reviewed on an ongoing basis by an SMC.

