## **6.5 Concomitant medication(s)/treatment(s)**

### **6.5.1 Permitted concomitant treatments (medications and therapies)**

The following concomitant medications are permitted during the study:

- Paracetamol/acetaminophen for the treatment of mild symptoms (eg, headache or other pain), given at most every 6 hours to 8 hours, not exceeding 2g per day, and with a total of no more than 5g over 7 days.
- Ibuprofen, not exceeding 1.2g per day.
- Nasal corticosteroids for seasonal rhinitis and topical corticosteroids for controlled dermatological conditions.
- Oral contraceptives not exceeding 30µg ethinyl estradiol or postmenopausal hormonal replacement therapy (HRT) or implants, patches, or IUDs/IUSs delivering progesterone (for female study participants).

For all study participants: if a concomitant medication is required during the Washout Period and if there is no impact on the study participant's safety and the impact on quality of further study data is deemed to be minimal, the study participant can remain in the study after Sponsor approval. If the concomitant medication use does not violate these criteria and no drug allergy has been reported, the study participant will be permitted to continue in the study.

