### Highly effective contraceptive methodsa

Highly effective contraceptive methods that are user dependentb
Failure rate of <1% per year when used consistently and correctly.
Combined (estrogen and progestogen containing) hormonal contraception associated with inhibition of ovulation c 

• Oral

• Intravaginal

• Transdermal

Progestogen only hormonal contraception associated with inhibition of ovulation 

• Oral

• Injectable

Highly effective methods that are user independentc
Implantable progestogen only hormonal contraception associated with inhibition of ovulation 

• Intrauterine device (IUD)

• Intrauterine hormone-releasing system (IUS)

• Bilateral tubal occlusion

Vasectomized partner
A vasectomized partner is a highly effective contraception method provided that the partner is the sole male sexual partner of the WOCBP and the absence of sperm has been confirmed. If not, an additional highly effective method of contraception should be used.
Sexual abstinence
Sexual abstinence is considered a highly effective method only if defined as refraining from heterosexual intercourse during the entire period of risk associated with the study treatment. The reliability of sexual abstinence needs to be evaluated in relation to the duration of the study and the preferred and usual lifestyle of the participant.
NOTES:
a) In case of newly started contraception pills/IUDs, PI should consider the correct timing of starting/applying such methods in relation to the menstrual cycle and the manufacturing instruction as to when these newly started methods would become effective.
b) Typical use failure rates may differ from those when used consistently and correctly. Use should be consistent with local regulations regarding the use of contraceptive methods for participants participating in clinical studies.
c) Hormonal contraception may be susceptible to interaction with the IMP, which may reduce the efficacy of the contraceptive method. In this case, two highly effective methods of contraception should be utilized during the treatment period and for at least 1 week after the last dose of study treatment.

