## Pregnancy testing

- A WOCBP should only be included after a confirmed menstrual period and a negative highly sensitive serum pregnancy test at the Screening Visit.
- Additional urine pregnancy testing should be performed on Day -1 and at the SFU Visit after the last dose of study medication (and as required on all other occasions).
- Pregnancy testing will be performed whenever a menstrual cycle is missed or when pregnancy is otherwise suspected.
- A positive urine test should be confirmed by a blood test with a sensitivity of 25 mIU/mL.

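### Exclusion 11 reverses the 30µg ethinyl estradiol threshold that Section 6.5.1 sets for oral contraceptives

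*Protocol*

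**What the plan says.** Exclusion 11 (Protocol Section 5.2, prior/concomitant therapy) opens with a general bar. A woman is excluded if "Participant has received or intends to use any prescription or nonprescription medicines" within a stated interval before first dosing or during the clinical part, unless the medicine treats an adverse event. After a sentence on strong CYP3A4 inducers and inhibitors comes the exception: "This does not include oral contraceptives exceeding" 30µg ethinyl estradiol, followed by hormone replacement after menopause, implants, patches and intrauterine methods.

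Section 6.5.1, on permitted concomitant treatments, gives nearly the same list, but its oral line reads "Oral contraceptives not exceeding" 30µg ethinyl estradiol.

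Four other places bear on how the two lines work together:
- Inclusion 6 (Section 5.1) makes a woman of childbearing potential eligible as "A WOCBP who agrees to follow the contraceptive guidance in Appendix 4 during the treatment period and for at least 1 week", counted from her final dosing.
- Appendix 4 (Section 10.4) counts as highly effective "Combined (estrogen and progestogen containing) hormonal contraception associated with inhibition of ovulation", includes the oral route, and sets no ethinyl estradiol limit.
- Section 5 states that recruitment and enrollment criteria may not be waived in advance. Section 8 repeats that waivers are not allowed.
- SAP Section 6.1.4 treats the Section 6.5.1 list as the limit of what may be continued on study.

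**The concern.** The two contraceptive lines appear to be the same rule written twice, with the inequality reversed in one of them. That matters because an exclusion criterion is applied to each woman at Screening and again on Day -1 (Tables 1-3 and 1-4), and the site has no discretion to set it aside.

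A site following the text would turn away women whose pill the protocol elsewhere permits. It would let through women whose pill falls outside the permitted list. A site following the evident intention would enroll women who fail a written exclusion criterion and would have to record a deviation for each. Different staff could reasonably do either, so eligibility decisions for pill users would depend on who reads the page. Both parts of the study enroll women under this criterion.

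**Working it through.** The plan gives no figure to reproduce, and no sample-size or power calculation is involved. The check sets the rules side by side for a combined pill containing *d* µg of ethinyl estradiol.

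| Rule | d ≤ 30 | d > 30 |
|---|---|---|
| Exclusion 11, exception as written | Not exempt, so excluded as a user of a prescription medicine | Exempt |
| Section 6.5.1 permitted list | Listed | Not listed |
| SAP 6.1.4 (continuation limited to the 6.5.1 list) | Within the limit | Outside the limit |
| Section 6.5.2 prohibited list | Not named | Not named |
| Appendix 4, combined oral method | Accepted | Accepted |

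1. Exempt under exclusion 11: {d > 30}. Listed in Section 6.5.1: {d ≤ 30}. The intersection is empty. A pill of exactly 30µg falls on the lower side: it is listed but not exempt.
2. With *not* inserted, exclusion 11 exempts {d ≤ 30}. The intersection with Section 6.5.1 is then {d ≤ 30}, every dose up to and including 30µg.

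Two other readings of exclusion 11 were tried.
- *The exception qualifies only the preceding CYP3A4 sentence.* Every pill then stays under the general bar in the first sentence. Users of 30µg or less are still excluded, and the threshold still runs opposite to Section 6.5.1.
- *The last sentence lists what is disallowed.* A pill above 30µg would then be barred, which fits Section 6.5.1. But hormone replacement, implants, patches and intrauterine methods stand in the same sentence and would be barred with it. Section 6.5.1 permits all of these, and Appendix 4 accepts implants and intrauterine methods.

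The direction of the error can be settled from the text. The matching line in Section 6.5.1 sets 30µg as a ceiling. The paracetamol and ibuprofen lines beside it are also ceilings. SAP 6.1.4 defers to that section, and Appendix 4 accepts the oral combined method. A missing *not* in exclusion 11 reconciles all of these. Both wordings are current text, neither is affected by redaction, and the Amendment 1 summary lists no change to either section.

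**The case against.** The best case for leaving this alone is that it is an obvious slip. Section 6.5.1 and Appendix 4 show what was meant, other contraceptive methods remain available, and nothing in the analysis depends on it. Section 6.5.1 also lets a participant remain in the study, with Sponsor approval, when a medicine is needed during washout.

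Much of this stands, and it limits what can be claimed. A reader might infer that a pill above 30µg is forbidden and that its user must stop, switch or be withdrawn. The protocol does not say so. Section 6.5.2 names strong CYP3A4 interactors and medicines strongly affecting gastric pH, and no contraceptive. Withdrawal under Section 7.2 is tied to prohibited medicines. The protocol does not call the 6.5.1 list exhaustive; the limiting language is in the SAP, which is not a conduct rule for sites. Such a pill is unlisted, not prohibited.

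A reader might also infer avoidable pregnancy exposure, on the argument that a woman on a lower-dose pill would stop it to qualify. No text directs her to; read literally, she fails screening. The timing of the contraception requirement in inclusion 6 applies to every woman of childbearing potential and would not change with the correction. Safeguards exist as well: Appendix 4 requires a confirmed menstrual period and a negative serum test at Screening, then "Additional urine pregnancy testing should be performed on Day -1 and at the SFU Visit", with further testing if a cycle is missed or pregnancy suspected. Exclusion 24 bars women who are pregnant or planning pregnancy.

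What does not stand is the suggestion that site judgement is enough. The Sponsor-approval clause concerns a medicine needed during washout and does not amend an exclusion criterion. With waivers ruled out, acting on the evident meaning is itself a deviation.

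**Conclusion.** The inconsistency is real and is in current, operative text. Exclusion 11 inverts the 30µg threshold, so that, taken literally, it rejects the pill users whom Section 6.5.1 permits and exempts those whose pill it does not list. This rests on reading the exception as qualifying the whole criterion; on the narrower CYP3A4 reading, users of 30µg or less are rejected all the same.

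The reach is narrow: eligibility decisions and site conduct for women using combined pills, in both parts. The number affected cannot be estimated, because the documents do not say how many pill users are expected. The documents give no basis for a pregnancy-risk figure, and no effect on PK estimates, power or analysis sets is claimed. Confidence is high on the wording conflict and on the direction of the correction.

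**What to change.** In exclusion 11, insert *not* before *exceeding 30µg*, so that the exception matches the oral contraceptive line in Section 6.5.1. The cost is one word in a protocol amendment. Design, sample size and analysis are unchanged, and Section 6.5.1, Appendix 4 and SAP Section 6.1.4 need no edit for this point.

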#### **Prior/concurrent clinical study experience**

12. Participant has previously participated in this study or participant has previously been assigned to treatment in a study of the medication under investigation in this study.
13. Participant has participated in another study of a study medication (and/or an investigational device) within the previous 30 days or 5 half-lives, whichever is greatest, or is currently participating in another study of an study medication (and/or an investigational device).

## Diagnostic assessments

14. Participant has a medical history or current diagnosis of renal impairment and/or screening laboratory results show:
  - An estimated glomerular filtration rate (eGFR)  $<80\text{mL/min}/1.73\text{m}^2$  (using the Chronic Kidney Disease Epidemiology Collaboration formula)
  - An albumin/creatinine ratio  $\geq 30\text{mg}/\text{mmol}$
  - Participant has a urinary tract infection but could be rescreened once the infection has been resolved
  - Clinically significant electrolyte abnormalities
15. Participant has any clinically relevant abnormal findings in physical examination, laboratory tests, or vital signs, which, in the opinion of the Investigator, may place the participant at risk because of participation in the study.
16. Presence of hepatitis B surface antigen (HBsAg) at screening or within 3 months prior to dosing.
17. Positive hepatitis C antibody test (HCVAb) result at screening or within 3 months prior to starting study intervention. NOTE: Participants with positive HCVAb due to prior resolved disease can be enrolled if a confirmatory negative hepatitis C ribonucleic acid (RNA) test is obtained.
18. Positive hepatitis C RNA test result at screening or within 3 months prior to first dose of study medication. NOTE: Test is optional and participants with negative HCVAb test are not required to also undergo hepatitis C RNA testing.
19. Positive immunodeficiency virus antibody test (HIV1Ab and HIV2Ab) at screening.
20. Participant has alanine transaminase (ALT), aspartate transaminase (AST) or alkaline phosphatase (ALP) are greater than the upper limit of normal (ULN) at Screening.

For randomized participants with a baseline result  $>\text{ULN}$  for ALT, AST, ALP, or total bilirubin, a baseline diagnosis and/or the cause of any clinically meaningful elevation must be understood and recorded in the electronic case report form (eCRF).

If study participant has  $>\text{ULN}$  ALT, AST, or ALP that does not meet the exclusion limit at screening, repeat the tests, if possible, prior to dosing to ensure there is no further ongoing clinically relevant increase. In case of a clinically relevant increase, inclusion of the participant must be discussed with the Medical Monitor.

Tests that result in ALT, AST, or ALP up to 25% above the exclusion limit may be repeated once for confirmation. This includes rescreening.
21. Participant has bilirubin  $>1.5\times\text{ULN}$  (isolated bilirubin  $>1.5\times\text{ULN}$  is acceptable if fractionated and direct bilirubin  $<35\%$ ).
22. Current or chronic history of liver disease or known hepatic or biliary abnormalities (with the exception of Gilbert's syndrome or asymptomatic gallstones).

23. Participant has any clinically relevant electrocardiogram (ECG) finding at the Screening Visit or at Baseline, or a family history of sudden death due to long QT syndrome which, in the opinion of the Investigator, would put the participant at increased risk of QT prolongation during the study (See Section 7.1.2 for QTcF withdrawal criteria). In addition, any study participant with any of the following findings will be excluded at Screening: QT interval correlated for heart rate using Fridericia's formula >450 msec for males and 470msec for females; other conduction abnormalities (defined as PR>=220 ms), irregular rhythm other than sinus arrhythmia or occasional, rare supraventricular, and rare ventricular ectopic beats.

